10.4.3 ANALYSIS OF THE SECONDARY ENDPOINT(S)

Analysis of the secondary measure, number of body contacts will follow that same methods as described for the primary measure, number of collisions (all contacts). Number of body contacts will be expressed as the rate of body contacts per 100 true hazards per hour.

Rating scale responses from the device questionnaire will be summarized using descriptive statistics. Responses to open-ended questions will be examined for common themes and coded accordingly.

10.4.4 SAFETY ANALYSES

Our main measure of safety is the number and severity of collision incidents when using the device in everyday mobility. However, this is also our main measure of device efficacy. If the number and severity of collision incidents is reduced when the device is in active mode compared to the silent mode, this would suggest that the device is effective. However, if the number and severity of collisions is greater when the device is in the active than the silent mode, then this would suggest that the device is not

effective and the device warnings were in some way causing collisions (rather than helping to avoid collisions). Collision incidents will be summarized with descriptive statistics. Incidents will be classified in terms of severity using the scale described in section 8.2.1.

If a severe or serious adverse event occurs before the code for the silent/active mode is broken, a non-masked member of the study team will review the data recorded by the device to examine the events leading to the collision and will determine whether the collision occurred when the device was in the active or the silent mode.

Please also see section 8.

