4.2.3 EXPLORATORY ENDPOINTS

In addition to the primary and secondary outcome measures for the clinical trial, the collision warning device will collect a wealth of information about collision incidents. When imminent collisions are detected, video will be saved for each warning given by the device. These images will provide details about the nature and circumstances of near collisions and actual collisions of participants. These data will be valuable for increasing our knowledge about collision incidents of blind and visually impaired people in everyday mobility and will help guide the development of future mobility devices and training programs. Our O&M consultant will also review images from some typical cases to assess whether, in the future, a collision detection device with recording capabilities would be helpful in O&M training; in particular, for providing remote (long distance) training for clients in rural areas (e.g., the clients could send the images to the O&M instructor to review and provide feedback).

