8.2 CLASSIFICATION OF AN ADVERSE EVENT

8.2.1 SEVERITY OF EVENT

The following guidelines will be used to describe adverse event severity.

- **Mild** – Events require minimal or no treatment and do not interfere with the participant’s daily activities.
- **Moderate** – Events result in a low level of inconvenience or concern with the therapeutic measures. Moderate events may cause some interference with functioning.
- **Severe** – Events interrupt a participant’s usual daily activity and may require systemic drug therapy or other treatment. Severe events are usually potentially life-threatening or incapacitating.

For example if a subject has a minor collision with an object while walking when using the device which results in a little bruising or a minor cut, the event would be classified as mild.

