8.3 TIME PERIOD AND FREQUENCY FOR EVENT ASSESSMENT AND FOLLOW-UP

Study personnel will ask about AEs during the telephone follow ups and the final study visit at Schepens. These will be collected as solicited events.

In addition, participants will be instructed to contact study personnel between visits if an AE occurs. If a participant contacts a member of the study team to report an event between scheduled visits, the event will be collected as an unsolicited event. Double capture of events (captured both as an unsolicited and a solicited AE) will be avoided by asking the participant whether the event has already been reported (at a previous visit or between visits)

Information to be collected about each event includes event description, time of onset, study personnel's assessment of severity, relationship to study device(assessed only by PI), and time of resolution/stabilization of the event. All AEs occurring while on study will be documented appropriately regardless of relationship. All AEs will be followed to adequate resolution.

Any medical condition that is present at the time that the participant is screened will be considered as baseline and not reported as an AE. However, if the study participant's condition deteriorates at any time during the study, it will be recorded as an AE. UPs will be recorded in the data collection system throughout the study.

Changes in the severity of an AE will be documented to allow an assessment of the duration of the event at each level of severity. AEs characterized as intermittent will require documentation of onset and duration of each episode.

The PI will record all reportable events with start dates occurring any time after informed consent is obtained until 7 (for non-serious AEs) or 30 days (for SAEs) after the last day of study participation. At each study visit, an investigator will inquire about the occurrence of AE/SAEs since the last visit. Events will be followed for outcome information until resolution or stabilization.

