10.4.2 ANALYSIS OF THE PRIMARY EFFICACY ENDPOINT(S)

The analysis will start with descriptive and graphical summaries of the rate of collision incidents (all contacts) in the active and silent modes, and the difference between active and silent modes. The rate will be computed as the rate of contacts per 100 true hazards (reviewed) per hour. The rate computation takes account of both duration of use and number of true hazards encountered, since some subjects might walk for longer but encounter fewer hazards while others might encounter more hazards in a shorter duration. Contacts will include all contacts with the collision hazard, either with their mobility aids (such as long cane) or body (touching with hand, bumping into the obstacle).

The primary analysis will start by comparing the within-subject difference in the rate of collisions (all contacts) between the active and silent modes using a Wilcoxon Signed-Rank test.

Next a model will be constructed to evaluate within-subject differences in the rates of collisions taking account of other factors that might affect the primary outcome measure. Since the number of contacts will represent overinflated count data, negative binomial regression models – considered to be more appropriate than Poisson regression models for such distributions – will be used for evaluating the association between rate of contacts and device operating condition (active vs. silent). In actual implementation of the regression model, the outcome will be set as the number of contacts (all contacts), while the exposure variable consisting of the duration of device use and the number of true hazards will be the offsets, and the estimated regression coefficients will be expressed as the rate ratio (β). The role of other possible predictors that could potentially affect the rate of contacts will be analyzed. These predictors will be taken from four broad categories: device data, demographics, vision characteristics, and mobility characteristics. Each predictor will be evaluated individually in a generalized mixed effects modeling framework (because we want to estimate within-subject effects) that will also include device condition. Any significant predictors ($p < 0.05$) and possible confounders (causing $\geq 10\%$ change in the rate ratio for the device condition predictor) will be selected for inclusion in the final model to determine the effect of device condition on rate of contacts.

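### Collision severity, half of the main safety measure, is graded on the adverse-event scale, which is unlikely to discriminate between modes and whose criteria are not described as collected per contact

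*Combined protocol and SAP*

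**What the plan says.** - Section 10.4.4 states: "Our main measure of safety is the number and severity of collision incidents when using the device in everyday mobility". Lower values in active mode are to be read as a working device, higher values as a sign that the warnings themselves cause collisions. The grading rule is: "Incidents will be classified in terms of severity using the scale described in section 8.2.1". The summary is descriptive; no test or decision rule is given for severity.
- Section 8.2.1 defines mild by the words "Events require minimal or no treatment and do not interfere with the" participant's daily activities. Moderate allows some interference with functioning, and severe means that usual activity is interrupted. The one worked example is a minor collision "which results in a little bruising or a minor cut, the event would be classified as mild".
- Section 10.4.2 defines the incidents: "Contacts will include all contacts with the collision hazard, either with their mobility aids (such as long cane) or body (touching with hand", and the same bracket goes on to include bumping into the obstacle.
- Section 4.2.3 gives the record of each incident: "When imminent collisions are detected, video will be saved for each warning given by the device".
- Section 8.3 gives the source of injury information: "Study personnel will ask about AEs during the telephone follow ups and the final study visit at Schepens". Participants may also report between contacts. Each reported event receives a severity grade and an onset time.
- Sections 4.2.2 and 10.4.3 make body contacts by mode a secondary endpoint, analysed like the primary.
- Section 10.6.1 codes all device data as mode A or B. Section 10.4.4 has a non-masked team member look up the mode of a severe or serious event that occurs before the code is broken.
- Section 10.1 says that no formal SAP will be written, so no further document settles these points.

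**The concern.** The grading rule joins two things that do not fit. The incidents are contacts seen in device recordings, many of them trivial by design because cane and hand contact count. The scale asks what happened to the person afterwards, which a clip from a chest-worn camera does not record.

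At stake is the reading of the safety result. Section 10.4.4 gives severity equal standing with number. If nearly all contacts fall in one grade, the report will show similar severity in both modes, and that may be taken as evidence that the warnings do not make collisions worse. The measure would have had little chance of showing otherwise.

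**Working it through.** The documents state no severity rate, distribution or power, so there is no figure to reproduce. The check sets the definitions side by side and then gauges sparseness under stated assumptions.

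**1. What each instrument separates**

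| Contact | Grade under 8.2.1 | Body-contact endpoint |
|---|---|---|
| Mobility aid only | Mild (nothing to treat) | Not counted |
| Hand touch | Mild | Counted |
| Bump without injury or interference | Mild | Counted |
| Minor collision with slight bruise or cut | Mild (worked example) | Counted |
| Collision that interferes with functioning | Moderate or severe | Counted |

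The first four rows share one grade, and the scale has no level for a contact without consequence. The secondary endpoint splits row 1 from the rest. Nothing splits row 2 from row 3. The exploratory categories in 10.4.11 are examples such as location, moving or stationary object, and object type; severity is not among them.

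**2. Whether the criteria are observed**

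Contacts come from device data and reviewed video (4.2.3, 10.4.2). Treatment and interference would come to light only through adverse-event reports (7.3.3, 7.3.4, 8.3). No section describes either item as recorded per contact.

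**3. Two readings of the word incident in 10.4.4**

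- If it means contacts, each has a mode code, but the grading criteria are unobserved and most contacts fall in the lowest grade by definition.
- If it means reported adverse events, each has a grade, but no written step assigns mild or moderate ones to a mode.

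On neither reading does the text lead to a usable severity-by-mode table.

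**4. How sparse the informative grades could be (illustration only)**

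Let T be total contacts over both modes and q the share above mild; both are assumed. The number of above-mild events M is taken as Poisson with mean T × q. With equal exposure and the active rate half the silent rate, each event falls in active mode with probability 0.5 / (1 + 0.5) = 1/3. The comparison is an exact two-sided binomial test against 1/2.

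The smallest possible p-value with M events is 2 × 0.5^M: 0.0625 for M = 5 and 0.031 for M = 6. So at least six events, all in one mode, are needed for p < 0.05.

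| T | q | Expected above mild | Power |
|---|---|---|---|
| 500 | 1% | 5 | 3% |
| 2000 | 1% | 20 | 25% |
| 500 | 5% | 25 | 31% |
| 2000 | 5% | 100 | 91% |

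Events are treated as independent; clumping within participants would generally lower these values. The plan has no such test, so the figures only gauge how much information the upper grades could carry.

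**The case against.** The strongest reply has four parts.

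- **The scale is not degenerate.** A reader might infer that severity by mode cannot show a difference at all. The documents do not support that. Moderate and severe grades exist, a hard bump that disturbs functioning need not be mild, and the last row of the power table shows that a difference could emerge if above-mild events were common enough. This part stands.
- **Body contacts are already compared by mode.** A reader might infer that a shift from cane taps to body bumps would go unnoticed. It would not: the secondary endpoint in 4.2.2 and 10.4.3 picks it up. What remains hidden is a shift within body contact, because 10.4.2 puts hand touch and bump together.
- **Mode is not lost for lesser events.** A reader might infer from 10.4.4 that only severe or serious events can ever be tied to a mode. That sentence covers review before the code is broken; device data carry an A or B code and reported events an onset time. This stands as to possibility, but the matching step is not written down.
- **The consequence is limited.** The summary is descriptive, and a report that most incidents were mild is a legitimate safety result. That is fair for overall safety. It does not answer the comparison by mode that 10.4.4 itself sets up.

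**Conclusion.** The point holds in a limited form. Section 10.4.4 names an instrument ill suited to grading contacts: its criteria are not described as collected per contact, and its lowest grade runs from a cane tap to a minor collision with slight injury. The severity summary is unlikely to discriminate between active and silent modes, and the plan has no step matching reported mild or moderate collision-related events to a mode.

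The size cannot be stated from the documents, which give neither the expected number of contacts nor the share above mild. That most contacts would be graded mild is an inference from the definitions and the worked example. The power figures rest on assumed counts, equal exposure and a halved rate.

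This is worth correcting because severity is half of the stated main safety measure. It does not touch the primary endpoint, its analysis or the sample size.

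**What to change.** In 10.4.4:

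1. Keep the 8.2.1 scale for adverse events only, unchanged.
2. For contacts, have the clip reviewers code an ordinal grade from the saved video, for example: aid-only contact; hand touch; bump with the body; bump with visible stop, stumble or fall; plus a category for not gradable. Use sensor traces only if they are stored, which the documents do not state. Say explicitly that reviewers are masked to mode, since 10.6.1 names only participants and the investigators doing the statistical analyses. This presumes that clips are kept in silent mode too; say so.
3. Summarise the grade descriptively by coded mode A or B.
4. Use the onset time already collected under 8.3 to match every collision-related adverse event, of any grade, to mode A or B, and tabulate by mode. Show events with vague onset as mode unknown. Section 10.6.1 does not say whether A means the same mode in every participant; if it does not, match while masked and tabulate when the code is broken.

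The cost is one extra code per reviewed contact, slightly more review time, and some contacts that cannot be graded or events that cannot be assigned. Whether a chest-worn camera shows enough to score the grade is not established in the documents, so try it on a sample of clips first. Matching on the masked codes needs no early unblinding.

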10.4.5 ADHERENCE AND RETENTION ANALYSES

The amount that the collision warning device is used each day will be recorded by the device and will be summarized with descriptive statistics. The number of participants who withdraw from the study after visit 1, after visit 2, and after starting to use the device at home will be recorded and summarized with descriptive statistics.

10.4.6 BASELINE DESCRIPTIVE STATISTICS

Baseline descriptive statistics will be used to describe subjects included in analyses in regards to age, gender, and mobility.

10.4.7 PLANNED INTERIM ANALYSES

10.4.7.1 SAFETY REVIEW

Please see sections 5.5, 8.5 and 8.6

Adverse events will be monitored on an ongoing basis throughout the study. Administration of the study device will be halted immediately if there is a serious adverse event or a serious unanticipated problem. There are no statistical rules to halt enrollment.

10.4.7.2 EFFICACY REVIEW

An informal interim analysis will be conducted after about one-half of the subjects have completed the study. One of the masked study team members will conduct the analysis. The results of the analysis will be reported to the Safety Monitor and also to the Department of Defense, in a quarterly or annual report.

10.4.8 ADDITIONAL SUB-GROUP ANALYSES

Please see section 10.4.2 (analysis of primary efficacy endpoint).

10.4.9 MULTIPLE COMPARISON/MULTIPLICITY

Correction for multiple comparisons will be used when appropriate.

10.4.10 TABULATION OF INDIVIDUAL RESPONSE DATA

It is very unlikely that we will list individual data by measure and time point. If individual data are listed, the data will be totally de-identified.

10.4.11 EXPLORATORY ANALYSES

Data about collisions incidents during the period of using the device at home will be examined and a method of categorizing the incidents will be developed. For example, considering factors such as the location of the incident (e.g., indoors or outdoors), whether the collision object was stationary or moving, and the nature of the object (pedestrian, wall, overhang, etc.). The effect of factors such as level of vision loss, age, gender, activity level and walking speed will also be examined.

10.5 SAMPLE SIZE

Justification for our sample size estimate is provided by the results of the prior obstacle-course study with the first prototype device (Shrinivas, Tomasi and Luo, 2014). Although collision incidents on the course were much higher than in real-world mobility, the results nevertheless demonstrate our ability to measure significant device effects with a cohort of only 24 participants. Specifically, in the 13 tunnel vision patients in that study, an average effect size of 0.4 related to walking with the device was observed (pairwise difference between the conditions), with 0.38 as the standard deviation of change. Assuming that the effect size is halved (0.2) to account for real-world mobility, the standard deviation of change remains the same, $\alpha = 0.05$, and power of 0.8, we get a sample size of 31. With a 30% attrition rate (assuming multi visit study may have higher attrition), we arrive at the final sample size of 42.

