We agree to ensure that all staff members involved in the conduct of this study are informed about their obligations in meeting the above commitments.

Principal Investigators: [name] and [name]

Signed:

Date:

A signed statement of compliance has been uploaded as a separate document

PROTOCOL SUMMARY

Title: Wearable Collision Warning Device for Blind and Visually Impaired: Clinical Trial

Précis: A total of 42 participants with visual impairment or blindness will be trained to use a collision warning device that alerts them to impending collisions. They will use the device at home during their everyday mobility for about 1 month with weekly calls from a researcher. The device will operate in two modes: active mode (intervention condition), when it gives warnings and, silent mode (control condition), when it does not give warnings. The device will be programmed to generate a different randomized active/silent schedule for each subject. Participants will not know whether it is in the active or silent mode. The number of collisions in the 2 device modes will be compared.

Objectives: Our overall objective is to establish a strong evidence base for the functional efficacy of our novel collision warning device. We hypothesize that the device will reduce the number of collision incidents experienced by visually-impaired and blind patients in their daily activities.

Specific aims (as detailed in the grant):

- (1) Develop clinical study devices that have data recording functions, dispense the devices to patients for home use, and evaluate the efficacy of the device in the actual operational environment based on number of collision incidents.
- (2) Characterize device reliability performance.
- (3) Use questionnaires to record patients' perspectives on the utility and functionality of the device.

Secondary Objectives:

- (1) Quantify nature and frequency of collision hazards in the operational environment.
- (2) Assess potential of the device as a tool for future use in orientation and mobility training programs.

Endpoint Primary Endpoint: The primary outcome measure will be the difference in the number of collision incidents (defined as all contacts) in the active and silent modes. Fewer collision incidents during the active warning mode than the silent mode will indicate an effective intervention; the intervention benefit will be quantified by the percentage reduction in collision incidents.

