2 INTRODUCTION: BACKGROUND INFORMATION AND SCIENTIFIC RATIONALE

2.1 BACKGROUND INFORMATION

This clinical trial evaluates a novel collision warning device invented by [name] and colleagues. The device provides tactile warnings of potential collisions.

Prior studies of the collision warning device

A prototype of the portable collision warning device was previously evaluated in a lab-based clinical study in which participants were given brief training in how to use the device and then walked through an indoor obstacle course (in a large room) both with and without the device. The course included a high density of soft obstacles that would not cause any injury if a participant made contact with them

(including inflatable plastic trees and paper objects hanging from the ceiling). Participants included 13 subjects with tunnel vision (peripheral field loss) and 12 subjects with hemianopia (loss of half the field of vision in both eyes). The number of contacts with the obstacles was significantly lower when using the device than when walking through the course without the device (Pundlik, Tomasi and Luo, 2014). There were no adverse events. These results demonstrate preliminary efficacy and safety of the device within a controlled environment.

Pilot study to be conducted before the clinical trial

The prior study only evaluated the collision device within the indoor setting of our lab. Therefore, before starting the clinical trial, we will conduct a small pilot study of the device in which people with peripheral field loss or blindness/severe vision loss will take the device home and use it in their everyday mobility (as we plan to do for the clinical trial). The protocol for this pilot study has already been approved by the local IRB at Massachusetts Eye and Ear and also by the Department of Defense. Recruitment for the pilot study has started. The pilot study will provide data on the safety and potential efficacy of the device in everyday use in an uncontrolled environment. Data from the pilot study will be used to finalize the design of the clinical trial and verify the sample size calculation.

Prior studies of other electronic travel aids

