5.4.2 HANDLING OF PARTICIPANT WITHDRAWALS OR TERMINATION

If a participant withdraws or is terminated from the study, they will be asked to return the device and, if willing, complete a questionnaire about their experience with the device.

Our sample size estimate includes an allowance for withdrawal/attrition. If more participants withdraw than anticipated, additional participants will be recruited to ensure we reach our target enrollment to complete the clinical trial.

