10.3 ANALYSIS DATASETS

The dataset for the analysis of the primary efficacy outcome measure will be a modified intention-to-treat dataset. Only participants who have completed the home-use part of the study will be included in the analysis.

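### Section 10.5: 31 evaluable, 30% attrition and 42 enrolled do not agree; at 30% attrition, 42 leaves about 29 completers and paired-t power of 0.78

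*Combined protocol and SAP*

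**What the plan says.** Section 10.5 takes a mean paired difference of 0.2 and an SD of change of 0.38, with alpha 0.05, "and power of 0.8, we get a sample size of 31". It continues: "With a 30% attrition rate (assuming multi visit study may have higher attrition), we arrive at the final sample size of 42".

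Four other places bear on how these figures are read:

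- **Protocol Summary, Précis:** "A total of 42 participants with visual impairment or blindness will be trained to use a collision warning device". The Population entry in the same summary also gives 42.
- **Section 10.3:** "Only participants who have completed the home-use part of the study will be included in the analysis".
- **Section 5.4.2:** "Our sample size estimate includes an allowance for withdrawal/attrition", followed by "If more participants withdraw than anticipated, additional participants will be recruited to ensure we reach our target enrollment to complete the clinical trial".
- **Section 2.1:** "Data from the pilot study will be used to finalize the design of the clinical trial and verify the sample size calculation".

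Section 10.5 names neither the test nor the sidedness. The alternative hypothesis in 10.2 is two-sided. The primary analysis in 10.4.2 compares rates "between the active and silent modes using a Wilcoxon Signed-Rank test".

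**The concern.** The three linked figures in 10.5 (31 needed, 30% lost, 42 enrolled) cannot all hold, and the documents do not say how 42 was reached. A reader will take 42 to protect 31 completers and power of at least 0.8 at the attrition rate stated beside it. It does not.

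The mismatch carries into 5.4.2. Replacement there starts when withdrawals pass the anticipated level, and 10.5 implies two such levels: 11 withdrawals (42 − 31) or 12.6 (30% of 42). The target in that sentence can also be read as 42 enrolled or as 31 completing. Staff could not say from the text at which withdrawal replacement begins.

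**Working it through.** **Inputs.** Difference 0.2, SD 0.38, alpha 0.05, power 0.8, attrition 30% and enrolment 42, all from 10.5. Two-sided testing is taken from the alternative hypothesis in 10.2, and analysis of completers only from 10.3.

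**Step 1: reproduce 31.** For a paired t-test on n differences, power is the probability that a non-central t variable, with n − 1 degrees of freedom and non-centrality √n × 0.2/0.38, falls outside the two-sided 5% critical values.

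| n | Non-centrality | Power |
|---|---|---|
| 29 | 2.834 | 0.781 |
| 30 | 2.883 | 0.796 |
| 31 | 2.930 | 0.809 |

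The smallest n with power of at least 0.8 is 31, so the plan's figure reproduces. A one-sided t-test would need 24.

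**Step 2: from 31 to enrolment.**

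- Correct allowance: 31/(1 − 0.30) = 44.3, so 45.
- Common shortcut: 31 × 1.30 = 40.3, so 41.

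Neither gives 42.

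**Step 3: what 42 delivers at 30%.** 42 × 0.70 = 29.4, about 29 completers, with power 0.781. At SD 0.38 the difference detectable with power 0.8 is 0.205 with 29 completers, against 0.198 with 31.

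**Step 4: what attrition 42 can bear.** 42 − 31 = 11 withdrawals, and 11/42 = 26.2%.

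**Step 5: the planned test.** The power of the Wilcoxon signed-rank test depends on the distribution of the differences, which the protocol does not give. If they are normal (an assumption), simulated power is about 0.76 with 29 completers and 0.79 with 31. The gap between the two sample sizes is about the same as for the t-test.

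**The case against.** Five points can be made for the plan.

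- **Section 5.4.2 nearly closes the gap.** Thirty per cent of 42 is 12.6, and 13 withdrawals is 31.0%. Read strictly, the thirteenth withdrawal already exceeds the anticipated level and triggers replacement. At most 12 are then lost unreplaced, leaving 30 completers and power 0.796. This is a fair reading, and on it the shortfall is one completer and about 0.4 points of power. The protocol does not fix that reading, however, and 30 is still below the stated 31.
- **The denominator of the 30% is not defined.** The Précis counts 42 people trained, while section 10.4.5 also tracks withdrawals after Visit 1, before training. If part of the 30% falls before training, fewer than 12.6 of the 42 are lost. This stands as an ambiguity. But 10.5 applies the whole 30% in arriving at 42, and the summary gives 42 as the study population, so applying 30% to 42 is the natural reading.
- **42 may come from another formula.** The two-sided normal approximation gives (1.960 + 0.842)² × (0.38/0.2)² = 28.3, so 29, and 29/0.7 = 41.4, so 42. That may be the origin of 42, but the text prints 31.
- **The pilot will verify the calculation.** Section 2.1 plans this, but 10.5 as it stands still prints all three figures.
- **The inputs are far less certain than two points of power.** The effect was halved by assumption and the SD carried over from an obstacle course. This is true, and it is why the point is minor.

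**Conclusion.** The concern holds as a minor arithmetic inconsistency. The evaluable number of 31 is sound, and the error lies only in the step to 42. At the plan's own 30%, 42 enrolled gives about 29 completers and power of 0.78, which is two points below the stated 0.8 and three below the 0.81 that 31 completers would give. On the strict reading of 5.4.2 it gives 30 completers and just under 0.80.

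These figures assume a two-sided paired t-test, which reproduces 31, the difference and SD stated in 10.5, and attrition counted from the 42. The loss of power would not threaten the trial. The practical consequence is that the replacement trigger in 5.4.2 cannot be applied until the figures agree.

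**What to change.** Keep 42 and replace the last sentence of 10.5 with wording such as:

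> With 42 enrolled and 30% attrition, about 29 participants are expected to complete, giving power of about 0.78 (two-sided paired t-test, difference 0.2, SD 0.38). Thirty-one completers (power 0.81) are reached if no more than 11 participants (26%) withdraw.

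State at which visit a participant begins to count towards the 42.

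In 5.4.2, give the anticipated withdrawals as a whole number and say whether the target is participants enrolled or participants completing. Thirty per cent of 42 is 12.6. If this is rounded to 13, replacement starts at the fourteenth withdrawal and the 29 above stands. If 12 is chosen, replacement starts at the thirteenth, and 10.5 should say 30 completers and power 0.80 (0.796).

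The cost is wording only: no extra participants, visits or device time, and a stated power slightly less favourable than now. Two other routes would also make the figures agree. Enrolling 45 honours the 30% exactly, but adds three participants, each needing about a month with one of only 4 devices, for a small gain. Changing 30% to 26% fits the assumption to the chosen sample size and drops the caution that 10.5 gives as its reason for 30%. Neither is needed.
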